DOCUMENT TITLE: A Prospective, Post-Market, Multi-Center Study Evaluating ViBone in Cervical and Lumbar Spine Fusion	DOCUMENT NUMBER: CLP-0001
--	---	-------------------------------------

A Prospective, Post-Market, Multi-Center Study Evaluating ViBone® in Cervical and Lumbar Spine Fusion

Clinicaltrials.gov Identifier:

NCT03425682

Original Protocol Version Date: 11/17/2017

Sponsor:
Aziyo Biologics, Inc.
Corporate Headquarters
[name]
[name] 20904

Sponsor contact:
[name]
[contact]
[contact]

	DOCUMENT TITLE: A Prospective, Post-Market, Multi-Center Study Evaluating ViBone in Cervical and Lumbar Spine Fusion	DOCUMENT NUMBER: CLP-0001
--	---	-------------------------------------

Protocol Synopsis

Company:	Aziyo Biologics, Inc.
Protocol Number:	CLP-0001
Product:	ViBone® Viable Bone Matrix
Protocol Title:	A Prospective, Post-Market, Multi-Center Study Evaluating ViBone in Cervical and Lumbar Spine Fusion
Treatment Indication:	Spondylosis, spondylolisthesis, degenerative disc disease, or herniated nucleus pulposus affecting either 1 to 3 contiguous levels between C2 and C7 (for cervical patients) or L1 and S1 (for lumbar patients).
Purpose:	
The purpose of this study is to assess clinical and radiographic outcomes in patients who undergo 1-3 level anterior cervical discectomy fusion (ACDF) or lumbar interbody fusion (TLIF, PLIF, ALIF, LLIF) using ViBone. Subjects will be followed for 12 months following surgery to determine the number of study subjects that are solidly fused at or before 12 months postoperatively.
 
The data for cervical and lumbar fusions will be analyzed separately and will be compared to published and/or retrospective data for autograft or other similar graft materials.

Design:	
Up to 50 patients undergoing ACDF using ViBone will be enrolled.
 
Up to 50 patients undergoing lumbar interbody fusion using ViBone will also be enrolled.
 
Subjects will be followed via the enrolling center's standard of care for the procedure.
 
Data from patients meeting the study criteria will be gathered at baseline, 6 months, and 12 months post-surgery.

	DOCUMENT TITLE: A Prospective, Post-Market, Multi-Center Study Evaluating ViBone in Cervical and Lumbar Spine Fusion	DOCUMENT NUMBER: CLP-0001
--	--	-------------------------------------

Patient Population:	
Included are both male and female patients, 18-80 years of age with spondylosis, spondylolisthesis, degenerative disc disease, or herniated nucleus pulposus affecting 1, 2, or 3 contiguous levels of the spine between C2 and C7 (for cervical patients) or L1 and S1 (for lumbar patients).
 
Patients must be undergoing ACDF or lumbar interbody fusion using ViBone to be eligible for the study.

Outcome Measures:	
Primary:
 
 Incidence of successful fusion measured radiographically by 12 months post-surgery 
Secondary:
 
 Incidence of successful fusion measured radiographically by 6 months post-surgery Oswestry Disability Index (ODI)/Neck Disability Index (NDI) relative to baseline. Visual Analog Scale (VAS) relative to baseline. Incidence of subjects experiencing ViBone-related serious adverse reactions.
Duration:	Subjects will be evaluated via routine follow up visits through 12 months post-surgery.
Centers:	Up to 20 centers in the U.S.

	DOCUMENT TITLE: A Prospective, Post-Market, Multi-Center Study Evaluating ViBone in Cervical and Lumbar Spine Fusion	DOCUMENT NUMBER: CLP-0001
--	---	-------------------------------------

Study contact for discussion of protocol-specific issues:

[name]

Aziyo Biologics, Inc.

[contact]

Email: [contact]

**SAFETY REPORTING CONTACT INFORMATION:
REPORTING OF SAFETY INFORMATION TO SPONSOR**

Aziyo pharmacovigilance designee and contact information for adverse reaction reporting:

[name]

Aziyo Biologics, Inc.

[contact]

Email: [contact]

Table of Contents

1	ABBREVIATIONS	7
2	TRADEMARK STATEMENTS	8
3	INTRODUCTION	8
3.1	Spine Fusion	8
3.2	Viable Bone Allografts	8
3.3	Description of ViBone	8
4	STUDY PURPOSE AND OBJECTIVES	9
4.1	Study Purpose	9
4.2	Objectives	9
5	STUDY DESIGN	9
5.1	Design Summary	9
5.2	Patient Enrollment	9
6	PATIENT SELECTION	10
6.1	Study Population	10
6.2	Eligibility criteria	10
6.2.1	Informed Consent Form	10
6.2.2	Inclusion Criteria	11
6.2.3	Exclusion Criteria	11
7	STUDY PROCEDURES	12
7.1	Schedule of Assessments	12
7.2	Study Visits	13
7.2.1	Pre-Surgery Screening Visit	13
7.2.2	Surgical Procedure Visit	13
7.2.3	Follow-Up Visits	13
7.2.4	Subject Close-Out	14

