5 STUDY DESIGN

5.1 Design Summary

This study is a multi-center, post-market, prospective patient registry to evaluate the clinical and radiographic outcomes of ViBone in patients undergoing cervical or lumbar spine fusion. Data will be gathered for up to 50 subjects undergoing ACDF surgery and up to 50 subjects undergoing lumbar interbody fusion surgery using ViBone. Total enrollment is expected to be approximately 200 subjects. The purpose of this study is to assess clinical and radiographic outcomes in patients who undergo 1-3 level ACDF or lumbar interbody fusion surgery using ViBone. Subjects will be followed for 12 months post-surgery to determine the number of study subjects that are solidly fused at 12 months postoperatively. This data will be compared to published and/or retrospective data for autograft or other similar products.

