6 PATIENT SELECTION

6.1 Study Population

Up to 50 ACDF and up to 50 lumbar interbody fusion patients from up to twenty centers in the United States will be enrolled. The study population will consist of male and female patients, 18-80 years of age. Eligible patients should have spondylosis, spondylolisthesis, degenerative disc disease, or herniated nucleus pulposus. Cervical fusion patients shall undergo ACDF surgery using ViBone at 1 to 3 contiguous levels between C2 and C7. Lumbar fusion patients shall undergo lumbar interbody fusion surgery using ViBone at 1 to 3 contiguous levels between L1 and S1.

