6.2.2 Inclusion Criteria

In order to be eligible, patients are required to meet the following inclusion criteria:

- Male or female, 18-80 years of age
- For cervical cases – ACDF surgery at 1, 2, or 3 contiguous levels between C2-C7
- For lumbar cases – lumbar interbody fusion surgery at 1, 2, or 3 contiguous levels between L1-S1
- Patient signed Informed Consent Form with HIPAA Authorization
- Appropriate candidate for surgery
- Patient will adhere to the scheduled follow-up visits and requirements of the protocol
 - Routine patient exams include pre-operative, operative, and at least two post-operative visits (6 and 12 months post-surgery)
 - Pre-operative and post-operative visits include radiological examination (X-ray (required) and CT scan (if available))

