7.2.2 Surgical Procedure Visit

The Surgical Procedure Visit shall occur on the same day as the surgical procedure. The following information shall be collected during the Surgical Procedure Visit:

- Surgical procedure details including the type of fusion performed, spine levels involved, ViBone, and other products used.
- If another product is being used in the interbody space, at least 70% of the total volume should be ViBone.

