12 STATISTICAL CONSIDERATIONS

As this study is designed to assess the clinical and radiographic outcomes in patients who undergo cervical (ACDF) or lumbar (TLIF, PLIF, LLIF, or ALIF) spine fusion surgery using ViBone, statistics will be descriptive. Baseline demographic and clinical variables will be summarized. Frequencies and percentages with confidence intervals will be tabulated for surgical outcomes.

	DOCUMENT TITLE: A Prospective, Post-Market, Multi-Center Study Evaluating ViBone in Cervical and Lumbar Spine Fusion	DOCUMENT NUMBER: CLP-0001
--	---	-------------------------------------

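### The planned comparison of fusion rates with outside data has no matching or standardisation by number of treated levels, so level mix alone can look like a graft difference

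*Combined protocol and SAP*

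**What the plan says.** **Who is enrolled.** Section 6.2.2 admits "For cervical cases – ACDF surgery at 1, 2, or 3 contiguous levels between C2-C7" and "For lumbar cases – lumbar interbody fusion surgery at 1, 2, or 3 contiguous levels between L1-S1". No cap or quota by level count is given. Section 12 lists four approaches within the lumbar cohort (TLIF, PLIF, LLIF, ALIF).

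**What is analysed.** Section 12 makes the statistics descriptive and promises: "Frequencies and percentages with confidence intervals will be tabulated for surgical outcomes". The only split stated is cervical versus lumbar, in the Synopsis (Purpose) and again in Section 16.2.

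**What it is compared with.** The Synopsis says: "The data for cervical and lumbar fusions will be analyzed separately and will be compared to published and/or retrospective data for autograft" and comparable grafts. Sections 4.2, 5.1, 10 and 16.2 also plan an outside comparison. None of them asks for outside data with a similar level or approach mix, or for any adjustment.

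**What counts as success.** Section 5.1 follows subjects "to determine the number of study subjects that are solidly fused at 12 months postoperatively". Section 10 defines radiographic success for an interbody space. No rule turns the results at two or three levels into one result for the subject.

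**What is recorded.** Section 7.2.2 collects "Surgical procedure details including the type of fusion performed, spine levels involved, ViBone, and other products used".

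**The concern.** Setting the fusion result beside outside data is the declared use of that result. If the result is a proportion of subjects, and a multi-level subject must fuse at every treated level to count, the proportion falls as levels are added, even when the graft does equally well at each level. The cohort's rate then depends on how many one-, two- and three-level operations happened to enrol, and the outside rate depends on its own mix. Two rates can therefore differ with no difference between grafts, or agree when there is one. The confidence intervals promised in Section 12 describe sampling error and do not cover this.

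As written, whether to break results down by level, and which outside series to use, can be decided after the fusion results are known.

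**Working it through.** The documents give no expected fusion rate, no rate by level count and no level mix for either side. There is therefore no figure in the plan to reproduce, and every rate and mix below is an assumption.

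**Inputs from the documents.** One to three levels in each cohort (6.2.2); up to 50 subjects per cohort (12.1); subjects as the unit of the count (5.1); success defined per interbody space (10).

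**Assumptions.** A subject is fused only if every treated level is fused. The per-level fusion probability p is the same for ViBone and the outside graft. Levels within a subject are independent, except where a correlation is stated. Mixes are percentages of subjects with one/two/three levels.

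**Formulas.** Subject-level rate with k levels = p^k. Cohort rate = sum over k of (share with k levels × p^k). The spurious gap is the difference between two cohort rates that differ only in mix.

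**Worked case, p = 0.90.**
- Rates by level count: 0.900, 0.810 and 0.729.
- Mix 40/40/20: 0.4 × 0.900 + 0.4 × 0.810 + 0.2 × 0.729 = 0.830. Against an all-single-level benchmark of 0.900, the gap is 7.0 points below.
- Mix 80/15/5: 0.8 × 0.900 + 0.15 × 0.810 + 0.05 × 0.729 = 0.878. Against a 40/40/20 benchmark of 0.830, the gap is 4.8 points above.

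**Range over p.** Gap A is a ViBone mix of 40/40/20 against all single-level (ViBone looks worse). Gap B is a ViBone mix of 80/15/5 against 40/40/20 (ViBone looks better).

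| Per-level rate | Rates at 1, 2, 3 levels (%) | Gap A (points) | Gap B (points) |
|---|---|---|---|
| 98% | 98.0, 96.0, 94.1 | 1.6 | 1.1 |
| 95% | 95.0, 90.2, 85.7 | 3.8 | 2.6 |
| 90% | 90.0, 81.0, 72.9 | 7.0 | 4.8 |
| 90%, correlation 0.3 | 90.0, 83.7, 79.2 | 4.7 | 3.2 |
| 85% | 85.0, 72.2, 61.4 | 9.8 | 6.7 |

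The correlated row uses a beta-binomial model with a + b = 1/0.3 − 1 = 2.333 and a = 0.9 × 2.333 = 2.1. The two-level rate is 0.9 × 3.1/3.333 = 0.837, and the three-level rate is 0.837 × 4.1/4.333 = 0.792.

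**Milder and harsher mixes (independent levels).** For 60/30/10 against 50/35/15 the gap is only 0.3 points at 98% per level and 1.8 at 85%. For all single-level against equal thirds at 85% it is 12.1 points.

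**For scale.** If 45 of 50 subjects are fused, the exact 95% interval is 78.2% to 96.7%, a half-width of about 9.2 points. A gap from level mix would come on top of that uncertainty.

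**The case against.** Several objections carry weight.

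- **The plan does not prescribe a single pooled rate.** A reader might infer from the silence on strata that one crude rate per cohort will be reported. Section 12 does not say so and does not exclude tables by level. What the documents support is narrower: no breakdown by level is specified, and no like-for-like rule governs the comparison.
- **The all-levels rule is not in the documents.** Section 5.1 suggests it and Section 10 does not contradict it, but neither states it. If fusion were reported per interbody space, the p^k effect would vanish under the equal per-level rates assumed here. The gaps apply only to a subject-level result.
- **No single bias figure can be attributed to the trial.** It is tempting to headline a bias of 5 to 7 points. That corresponds to the 90%, independent-levels row with two contrasting mixes; higher per-level rates, correlation or closer mixes shrink it, and lower rates enlarge it.
- **Lumbar approach is unquantified.** A reader might infer that pooling four approaches also biases the comparison. No passage says that fusion differs by approach, and the documents allow no estimate.
- **The study is descriptive.** There is no test, margin or success criterion, so no formal error rate is affected. The risk is to interpretation.
- **Strata will be small.** With up to 50 subjects per cohort, three-level results may be too imprecise to interpret alone, and level matching leaves other case-mix differences in place.

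These points limit the size and wording of the concern. They do not supply the missing rule: the outside comparison is still planned, with nothing to keep level mix out of it.

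**Conclusion.** The point holds as a cheap improvement to the analysis plan. Each cohort mixes one-, two- and three-level surgery, and the outside comparison has no level matching or standardisation. A subject-level fusion rate can therefore differ from an outside rate through level mix alone, in either direction.

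For the two mix contrasts tabulated, the illustrative gap runs from about 1 point at 98% fusion per level to about 10 points at 85%. This rests on the all-levels rule, equal graft performance, independent levels (except in the correlated row) and assumed mixes. The documents confirm none of these, so the range should be quoted and not one value from it. They do not support saying that the plan commits to a crude pooled rate, or that lumbar approach adds a known bias.

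**What to change.** In Section 12:

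1. State that a subject is fused only if all treated levels are fused.
2. Report the level mix of each cohort.
3. Tabulate 12-month fusion with 95% confidence intervals by number of treated levels (1, 2, 3) within each cohort, and descriptively by approach within the lumbar cohort.
4. Make the main outside comparison level-matched, or reweight the outside level-specific rates to the ViBone level mix.
5. Where an outside source cannot be split by level, allow the comparison but label it as unadjusted for level mix, and draw no conclusion about the graft from it.

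**Cost.** This is wording and analysis only, because Section 7.2.2 already collects levels and fusion type. Strata will be imprecise: with an assumed 30/15/5 split of 50 subjects, 27/30 fused gives an exact 95% interval of 73.5% to 97.9%, 13/15 gives 59.5% to 98.3%, and 4/5 gives 28.4% to 99.5%. Fewer outside sources will qualify for the main comparison.

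The direction of reweighting matters. Moving the outside rates to the ViBone mix leaves the ViBone estimate and its interval unchanged. Moving that 30/15/5 split to equal thirds instead, with assumed rates of 95/85/75%, would widen the ViBone half-width from about 8.3 to 14.3 points (normal approximation).

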1 ABBREVIATIONS

AATB	American Association of Tissue Banks
ACDF	Anterior Cervical Discectomy and Fusion
ALIF	Anterior Lumbar Interbody Fusion
Aziyo	Aziyo Biologics, Incorporated
BMI	Body Mass Index
BMP	Bone Morphogenetic Protein
C	Celsius
CFR	Code of Federal Regulations
CLIA	Clinical Laboratory Improvement Amendments
cm	Centimeter
CMS	Centers for Medicare and Medicaid Services
CRF	Case Report Form
CT	Computed Tomography
CV	Curriculum Vitae
DBM	Demineralized Bone Matrix
DDD	Degenerative Disc Disease
DMARD	Disease-Modifying Antirheumatic Drugs
DMSO	Dimethyl Sulfoxide
eCRF	Electronic Case Report Form
EDC	Electronic Data Capture
EoT	End of Treatment
FDA	Food and Drug Administration
FFDCA	Federal Food, Drug, and Cosmetic Act
GCP	Good Clinical Practice
HCT/P	Human Cellular and Tissue Based Product
HIPAA	Health Insurance Portability & Accountability Act
HIV	Human Immunodeficiency Virus
ICBG	Iliac Crest Bone Graft
ICF	Informed Consent Form
ICH	International Conference on Harmonization
IEC	Independent Ethics Committee
IRB	Institutional Review Board (includes ethics committee)
LLIF	Lateral Lumbar Interbody Fusion
NaCl	Sodium Chloride
NDI	Neck Disability Index
ODI	Oswestry Disability Index
PHI	Protected Health Information
PI	Principal Investigator
PLIF	Posterior Lateral Interbody Fusion
SOP	Standard Operating Procedure
TLIF	Transforaminal Lateral Interbody Fusion
VAS	Visual Analog Scale
WBC	White Blood Count

	DOCUMENT TITLE: A Prospective, Post-Market, Multi-Center Study Evaluating ViBone in Cervical and Lumbar Spine Fusion	DOCUMENT NUMBER: CLP-0001
--	---	-------------------------------------

2 TRADEMARK STATEMENTS

Aziyo® and ViBone® are registered trademarks of Aziyo, Inc.

3 INTRODUCTION

3.1 Spine Fusion

Degenerative disorders of the spine can lead to a multitude of clinical problems including pain, weakness, numbness, tingling and deformity. When conservative (non-surgical) treatment fails after at least a 6-month period and/or non-operative treatment is not indicated, patients and physicians may turn to a surgical solution. Surgical options consist of decompressing nerves, correcting and/or stabilizing deformities if required and fusing the segment, depending on the clinical situation. The "gold standard" for aiding healing in spinal fusion surgeries is the harvesting of autograft from the patient's iliac crest and placing it in and around the segments of the spine that are intended to be fused. Autograft is considered the "gold standard" because it contains the essential elements required for successful bone grafting: osteogenesis, osteoconduction, and osteoinduction.

However, the morbidity of harvesting autograft has been well documented and includes chronic donor-site pain, infection, neurologic injury, blood loss, deformity, bowel injury, hernia, and prolonged surgical and hospitalization time. There are now a number of products on the market to minimize or replace the use of autograft. However, few of these products contain all three essential bone-forming elements (osteogenesis, osteoconduction, and osteoinduction).

3.2 Viable Bone Allografts

ViBone is a human tissue allograft consisting of cryopreserved bone matrix that is aseptically processed to preserve native factors that support bone repair. ViBone is a Human Cellular and Tissue Based Product (HCT/P) per 21 CFR Part 1271. It is restricted to homologous use for transplant in procedures on a single occasion by a licensed physician or surgeon.

3.3 Description of ViBone

ViBone provides all three components critical for bone regeneration: osteoconductivity, osteoinductivity, and osteogenicity. It is a next generation cellular bone matrix that has been optimized to preserve the health of native bone cells and yield more readily available bioactive agents to enhance new bone formation while ensuring a safe allograft tissue for transplantation.

ViBone is supplied ready to use and must be stored in its original packaging at -75°C to -85°C until prepared for use. It is the responsibility of the transplant facility or clinician to maintain the allograft intended for transplantation in the appropriate recommended storage conditions prior to transplant. Refer to the package insert (Appendix 4) for warnings and precautions and usage instructions.

	DOCUMENT TITLE: A Prospective, Post-Market, Multi-Center Study Evaluating ViBone in Cervical and Lumbar Spine Fusion	DOCUMENT NUMBER: CLP-0001
--	---	-------------------------------------

4 STUDY PURPOSE AND OBJECTIVES

4.1 Study Purpose

The purpose of this prospective registry is to assess clinical and radiographic outcomes in patients who undergo ACDF or lumbar interbody fusion surgery using ViBone.

4.2 Objectives

Subjects will be followed for 12 months post-surgery to determine the incidence of successful fusion at 12 months postoperatively. This data will be compared to published and/or retrospective data for autograft or other similar products.

Additional study objectives include:

- Incidence of successful fusion measured radiographically at 6 months post-surgery
- Change from baseline in Oswestry Disability Index (lumbar interbody fusion patients) or Neck Disability Index (ACDF patients)
- Change from baseline in Visual Analog Scale for back and leg pain
- Incidence of ViBone-related serious adverse reactions

5 STUDY DESIGN

5.1 Design Summary

This study is a multi-center, post-market, prospective patient registry to evaluate the clinical and radiographic outcomes of ViBone in patients undergoing cervical or lumbar spine fusion. Data will be gathered for up to 50 subjects undergoing ACDF surgery and up to 50 subjects undergoing lumbar interbody fusion surgery using ViBone. Total enrollment is expected to be approximately 200 subjects. The purpose of this study is to assess clinical and radiographic outcomes in patients who undergo 1-3 level ACDF or lumbar interbody fusion surgery using ViBone. Subjects will be followed for 12 months post-surgery to determine the number of study subjects that are solidly fused at 12 months postoperatively. This data will be compared to published and/or retrospective data for autograft or other similar products.

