12.1 Sample Size

Up to 50 patients undergoing ACDF surgery using ViBone will be enrolled. Up to 50 patients undergoing lumbar interbody fusion surgery using ViBone will also be enrolled.

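### Section 5.1 expects about 200 subjects in total, but the cohort ceilings given there and in three other places allow at most 100

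*Combined protocol and SAP*

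**What the plan says.** The study size is given in four places in the combined protocol and SAP.

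- **Synopsis, Design row:** the cervical limit reads "Up to 50 patients undergoing ACDF using ViBone will be enrolled". The lumbar limit follows in the same form: "Up to 50 patients undergoing lumbar interbody fusion using ViBone will also be enrolled".
- **Section 5.1, Design Summary:** "Data will be gathered for up to 50 subjects undergoing ACDF surgery and up to 50 subjects undergoing lumbar interbody fusion surgery". The next sentence reads: "Total enrollment is expected to be approximately 200 subjects".
- **Section 6.1, Study Population:** both limits appear again, here together with the number of sites: "Up to 50 ACDF and up to 50 lumbar interbody fusion patients from up to twenty centers in the United States will be enrolled".
- **Section 12.1, Sample Size:** for the cervical cohort the text is "Up to 50 patients undergoing ACDF surgery using ViBone will be enrolled". The lumbar cohort has a matching sentence of its own: "Up to 50 patients undergoing lumbar interbody fusion surgery using ViBone will also be enrolled".

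Section 12 says that "statistics will be descriptive" and that percentages will be reported with confidence intervals. The synopsis and section 16.2 say that the cervical and lumbar data are analysed separately and compared with published or retrospective data.

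**The concern.** Two consecutive sentences in 5.1 give study sizes that cannot both hold. The per-cohort figures are maxima, so their sum bounds the total from above, and the expected total lies far above that bound.

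Two things are at stake. The first is operational. A site or IRB reading the protocol cannot tell whether enrolment closes at 100 or continues toward 200. Enrolling a 51st patient in either cohort would breach 6.1 and 12.1, yet a total near 200 cannot be reached without doing so.

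The second is what a reader infers about precision. The primary result is a fusion rate with a confidence interval in each cohort, so cohort size sets the width of that interval. Someone who takes 200 as the study size will expect narrower intervals than cohorts of at most 50 can give.

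**Working it through.** **Inputs from the documents**
- ACDF ceiling: 50 (synopsis, 5.1, 6.1, 12.1).
- Lumbar ceiling: 50 (same places).
- Cohorts enrolled: two. The comparator is published or retrospective data.
- Stated total: approximately 200 (5.1 only).
- Attrition or screen-failure rate, expected fusion rate, alpha, power: none stated.

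**Step 1: try to reproduce the total.** Maximum total = 50 + 50 = 100. The stated figure exceeds it by 200 − 100 = 100, and 200/100 = 2. The figure does not reproduce.

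**Step 2: look for a reading that gives 200.**
- *Attrition.* Inflating 100 for a loss fraction d gives 100/(1 − d), rounded up: 112 at d = 10%, 125 at 20%, 143 at 30%, 167 at 40% and 200 at 50%. Only a 50% loss reaches 200, and no loss rate is stated. The ceilings are also placed on patients enrolled, not on patients evaluable, so inflation would not apply to them.
- *Control or third cohort.* None is enrolled.
- *Centers.* Section 6.1 allows up to twenty centers but gives no number per center.
- *Ceilings of 100 per cohort.* 100 + 100 = 200 does reproduce the figure, but no passage gives such ceilings.

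**Step 3: effect on precision.** The fusion rates below are assumptions. The interval is the exact (Clopper-Pearson) 95% interval for x successes in n: lower limit = Beta(0.025; x, n − x + 1), upper limit = Beta(0.975; x + 1, n − x), where Beta(q; a, b) is the q quantile of the beta distribution. Half-width = (upper − lower)/2.

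| Evaluable per cohort | Assumed rate | x/n | 95% interval | Half-width (points) |
|---|---|---|---|---|
| 50 (all enrolled) | 90% | 45/50 | 78.2–96.7% | 9.2 |
| 50 | 80% | 40/50 | 66.3–90.0% | 11.8 |
| 50 | 70% | 35/50 | 55.4–82.1% | 13.4 |
| 40 (assumed loss of 10) | 90% | 36/40 | 76.3–97.2% | 10.4 |
| 40 | 80% | 32/40 | 64.4–91.0% | 13.3 |
| 100 (200 split evenly, assumed) | 90% | 90/100 | 82.4–95.1% | 6.4 |
| 100 | 80% | 80/100 | 70.8–87.3% | 8.3 |

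Using unrounded half-widths, the ratio of the 100-per-cohort reading to the best case under the ceilings is 6.36/9.24 = 0.69 at 90% and 8.26/11.84 = 0.70 at 80%. A reader relying on 200 would therefore expect intervals about 30% narrower than the ceilings allow.

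**The case against.** The strongest counter-argument is that this is one stray sentence with no inferential effect. The statistics are descriptive, the cohorts are analysed separately, and the pooled total is not the denominator of any planned fusion rate. Section 12.1, where a reader would look for the sample size, is clear and agrees with the synopsis and 6.1. The precision loss arises only for a reader who overlooks 12.1, splits 200 evenly and assumes a fusion rate. All of that is correct, and it limits the harm: the intervals above illustrate the point and do not show an error in any planned analysis. It does not remove the contradiction in the enrolment ceiling.

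A second argument is that 200 might loosely count patients who consent. Section 5.2 gives everyone who signs consent a screening number, and 7.2.4 foresees subjects with an ID who are never treated. This reading is weak. Section 5.1 calls the 200 enrolment, and the synopsis, 6.1 and 12.1 use the same term for the 50 + 50. Neither 5.2 nor 7.2.4 gives a number, and half of those consented would have to be lost before surgery.

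Two smaller points stand. Since 5.1 says approximately, the discrepancy is best described as about twofold. Also, the sample consent form was not available for this check, so whether it states a number of subjects is unknown.

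**Conclusion.** The concern holds. The total in 5.1 is about twice the maximum of 100 that the plan's own ceilings permit, and nothing in the text examined accounts for the difference. This conclusion needs only the sum 50 + 50 and rests on no assumption; words such as expected or approximately cannot bridge a twofold gap above a ceiling.

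Four places support 100 and one sentence supports 200, so the 200 is the outlier, but the documents do not prove which figure the sponsor intended. The precision comparison (9.2 against 6.4 points at 90%, 11.8 against 8.3 at 80%) does depend on assumptions: the fusion rates, full evaluability, and an even split of 200. The matter must be fixed because study size is a basic design figure that sites and IRBs rely on, even though no error rate or power claim changes.

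**What to change.** The sponsor should first confirm the intended study size.

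- **If the ceilings are right:** replace the sentence in 5.1 with: Total enrollment will be up to 100 subjects (up to 50 per cohort). This agrees with the synopsis, 6.1 and 12.1. It costs one sentence and adds no patients, visits or data.
- **If about 200 was intended:** change the ceilings in the synopsis, 5.1, 6.1 and 12.1 and state the split between cohorts. This would mean up to about 100 more subjects than the present ceilings allow.

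In either case, check that any subject number in the sample consent form agrees.

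Optionally, and separately from this correction, 12.1 could state the expected precision. If it does, the statement should be labelled as a best case with all 50 per cohort evaluable and an assumed fusion rate: an exact 95% half-width of about 9 points at 90% and about 12 points at 80%.
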